## **10.3.3 Evaluable Non-Target Disease Response:**

Participants who have lesions present at baseline that are evaluable but do not meet the definitions of measurable disease, have received at least one cycle of therapy, and have had their disease reevaluated will be considered evaluable for non-target disease. The response assessment is based on the presence, absence, or unequivocal progression of the lesions.

#### 10.4 STATISTICAL ANALYSES

## 10.4.1 General Approach

# 10.4.2 Safety data will be evaluated, as well as the MRD-free CR rate, in comparison to results from prior trials. Analysis of the Primary Endpoints

Meeting the primary safety endpoint will require treatment of 10 participants with no more than 2 DLT.

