#### 1 INTRODUCTION

## 1.1 STUDY OBJECTIVES

## 1.1.1 Primary Objective

To determine the safety and toxicity of moxetumomab pasudotox-tdfk and rituximab/Ruxience treated at the planned dose level, in participants with HCL and HCLv.

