#### 3.1.3 Dose Escalation

The original plan was to treat up to 10 participants at the 40 mcg/kg dose level, up to 16 total participants could have been required (including up to 10 participants at the 30 mcg/kg dose level) if there were 2 DLTs within the first 6 participants treated at the 40 mcg/kg dose. The accrual ceiling was set at 20 participants considering screen failures and/or inevaluable participants. Please refer to Section 10.2 for dose-escalation rules and below.

Initially, 3 participants were to be treated with moxetumomab pasudotox-tdfk 30 mcg/kg and rituximab 375 mg/m^2. If 0/3 had a DLT, then the next 3 participants would be treated with moxetumomab pasudotox-tdfk 40 mg/kg and rituximab 375 mg/m^2.

[figure not shown]
If 1/3 initial participants treated with 30 mcg/kg had a DLT, then 3 more would have been treated at 30 mcg/kg. If no more than 1 of the first 6 had a DLT, then 4 more participants were to have been enrolled at 30 mcg/kg provided that no more than a total of 2 of the 10 at the 30 mcg/kg level would have a DLT.

If participants were accrued to the 40mcg/kg level, if 0/3 or 1/3 had a DLT, then 3 more were to be treated using those dose levels. If no more than 1 of the first 6 had a DLT, then 4 more participants were to be enrolled provided that no more than 2 total of the 10 at the 40 mcg/kg level had a DLT with the exception of the types noted. If a 3rd participant had a DLT, accrual would end as soon as this is noted.

If 2 of the first 3 participants, or 2 of the first 6 participants, treated with moxetumomab pasudotox-tdfk 40 mcg/kg and rituximab 375 mg/m² had a DLT, then 3 additional participants were to be treated with moxetumomab pasudotox-tdfk 30 mcg/kg and rituximab 375 mg/m². If 0/3 or 1/3 of these next 3 had a DLT with these dose levels, then 4 more participants were to be enrolled at the 30 mcg/kg level provided that no more than 2 total of the 10 at the 30 mcg/kg level had a DLT. If 2 participants in the first 6 had a DLT at this level, then the trial would have ended accrual.

Furthermore, at any time in the 10 participants, if a 3rd participant had a DLT, accrual will also end as soon as that was noted.

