## 3.1.4 Dose Expansion

As of 9/24/21, 12 participants were enrolled, 3 that received moxetumomab pasudotox-tdfk at 30 mcg/Kg and 9 at 40 mcg/Kg. All participants were without DLT, therefore per protocol only 1 additional eligible participant treated with moxetumomab pasudotox-tdfk at 40 mcg/Kg could be enrolled, making a total of 13 eligible participants. After these participants, to better determine safety and efficacy, an additional 13 eligible participants will be enrolled and treated with moxetumomab pasudotox-tdfk at 40 mcg/Kg in combination with Ruxience instead of rituximab.

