#### 10.2 SAMPLE SIZE DETERMINATION

- The initial sample size determination: Up to 10 participants are intended to be treated in the trial using the following plan; if a different dose of moxetumomab pasudotox-tdfk is required, up to 16 participants will be needed to be enrolled.
  - Initially, 3 participants will be treated with moxetumomab pasudotox-tdfk 30 mcg/kg and rituximab 375 mg/m^2. If 0/3 have a DLT, then the next 3 participants will be treated with moxetumomab pasudotox-tdfk 40 mg/kg and rituximab 375 mg/m^2.

If 1/3 initial participants treated with 30 mcg/kg have a DLT, then 3 more will be treated at 30 mcg/kg. If no more than 1 of the first 6 have a DLT, then 4 more participants will be enrolled at 30 mcg/kg provided that no more than a total of 2 of the 10 have a DLT with the exception

Version Date: 04/16/2025

of the types noted. The upper one-sided 90% confidence bound on 2/10 is 45.0%. if a 3rd participant has a DLT, accrual will end as soon as this is noted.

If participants are accrued to the 40mcg/kg level, if 0/3 or 1/3 have a DLT (with the exception of the types noted), then 3 more will be treated using those dose levels. If no more than 1 of the first 6 have a DLT, then 4 more participants will be enrolled provided that no more than 2 total of the 10 have a DLT. The upper one-sided 90% confidence bound on 2/10 is 45.0%. if a 3rd participant has a DLT, accrual will end as soon as this is noted.

If 2 of the first 3 participants, or 2 of the first 6 participants, treated with moxetumomab pasudotox-tdfk 40 mcg/kg and rituximab 375 mg/m² have a DLT, then 3 additional participants will be treated with moxetumomab pasudotox-tdfk 30 mcg/kg and rituximab 375 mg/m². If 0/3 or 1/3 of these next 3 have a DLT with these dose levels, then 4 more participants will be enrolled at the 30 mcg/kg level provided that no more than 2 total of the 10 have a DLT with the exception of the types noted. If 2 participants in the first 6 have a DLT at this level, then the trial will end accrual. Furthermore, at any time in the 10 participants, if a 3rd participant has a DLT, accrual will also end as soon as this is noted. The upper one-sided 90% confidence bound on 2/10 is 45.0%.

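### The primary safety criterion still rests on 10 participants, so no result in the 13 Ruxience participants can change it, and no numeric DLT limit clearly applies to them

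*Combined protocol and SAP*

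**What the plan says.** The whole analysis of the primary endpoint is one sentence in section 10.4.2: "Meeting the primary safety endpoint will require treatment of 10 participants with no more than 2 DLT". Section 3.1.3 identifies the ten by dose, allowing enrolment to continue "provided that no more than 2 total of the 10 at the 40 mcg/kg level had a DLT". Section 10.2 supplies the only precision figure: "The upper one-sided 90% confidence bound on 2/10 is 45.0" percent.

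The primary objective (section 1.1.1, repeated in 10.1) is wider: "To determine the safety and toxicity of moxetumomab pasudotox-tdfk and rituximab/Ruxience treated at the planned dose level". Section 3.1.4 describes the position at the amendment: "12 participants were enrolled, 3 that received moxetumomab pasudotox-tdfk at 30 mcg/Kg and 9 at 40 mcg/Kg", all without DLT, with one more rituximab participant to come. It then says that "to better determine safety and efficacy, an additional 13 eligible participants will be enrolled", at 40 mcg/kg with Ruxience. The amended sample size in section 10.2 rests only on the comparison of MRD-free CR rates (26 against 64). It adds no safety criterion.

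The rule that a third DLT ends accrual appears in section 10.2 under the initial sample size plan, where every branch specifies rituximab, and in section 3.1.3, mostly in the past tense. Sections 3.1.4, 10.4.2 and 10.4.4 give no DLT count or bound for participants 14-26.

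**The concern.** The trial was doubled in size, and its second half receives a different anti-CD20 product. Safety is both the primary objective and a stated reason for the enlargement, yet the rule that decides the primary endpoint was left at its pre-amendment size. The trial could therefore report that its primary safety endpoint was met for rituximab/Ruxience on rituximab participants alone. Section 13.1 also lists the primary endpoint having been met as a possible ground for ending the study, so it matters which participants decide it.

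The second issue is accrual. If the third-DLT rule stops with the first ten participants at 40 mcg/kg, the Ruxience participants are enrolled without a prespecified count that would prompt a halt. If it continues, the text does not say whether the count restarts or accumulates.

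**Working it through.** **Inputs.** Ten participants and at most 2 DLTs (10.4.2); 0 of 9 with a DLT at 40 mcg/kg, with one rituximab participant to come (3.1.4); 13 on Ruxience at 40 mcg/kg (2.3.1, 3.1.4). Planned number at 40 mcg/kg: 10 + 13 = 23. With the 3 at 30 mcg/kg, the total is 26. I take the ten in 10.4.2 to be the ten at 40 mcg/kg, as 3.1.3 and 10.2 imply.

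**Step 1: reproduce the plan's figure.** The exact (Clopper-Pearson) one-sided 90% upper bound for x events in n is the 0.90 quantile of Beta(x+1, n−x). For 2/10, Beta(3, 8) gives 0.4496, which matches the stated 45.0%. The Wilson (39.8%), Wald (36.2%) and exact 95% (50.7%) bounds do not match, so the plan uses the exact 90% bound. I use it throughout.

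**Step 2: what could still change the criterion.** From 0/9, the tenth participant gives 0/10 (bound 20.6%) or 1/10 (33.7%). The criterion fails only at 3 DLTs among the ten. That would need at least two late DLTs among the nine already counted as DLT-free. Participants 14-26 do not enter the count.

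**Step 3: what the Ruxience participants could show.** Suppose the first ten finish with no DLT.

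| DLTs on Ruxience | Proportion of 13 | Upper bound, 13 | Pooled upper bound, 23 | Criterion in 10.4.2 |
|---|---|---|---|---|
| 0 | 0% | 16.2% | 9.5% | met |
| 3 | 23.1% | 44.4% | 26.8% | met |
| 4 | 30.8% | 52.3% | 31.8% | met |
| 6 | 46.2% | 66.9% | 41.3% | met |
| 13 | 100% | 100% | not computed | met |

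For zero events the bound is 1 − 0.10^(1/n): 20.6% for n = 10, 16.2% for n = 13 and 9.5% for n = 23. The row with 6 DLTs shows why the 13 need their own line: pooled, they appear as 6/23 = 26.1%.

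**Step 4: what the ambiguity in the accrual rule amounts to.** The table gives the probability of reaching a third DLT at assumed true rates, from the binomial distribution.

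| True DLT rate | Third DLT within 10 | Third DLT within 13 | No rule |
|---|---|---|---|
| 10% | 7.0% | 13.4% | 0 |
| 20% | 32.2% | 49.8% | 0 |
| 30% | 61.7% | 79.8% | 0 |
| 40% | 83.3% | 94.2% | 0 |

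A count accumulated over all 23 behaves like the 13 column if the first ten finish with none. These figures cover only the third-DLT provision and omit the separate provision for two DLTs among the first six. They show that the possible readings differ materially, and do not recommend one.

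**The case against.** Four points can be made for the plan.

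- **Oversight exists.** Any DLT takes that participant off study therapy (3.3). The team meets weekly, and decisions on dose-level enrolment use earlier toxicity data (7.4.1). The Safety Monitoring Committee reviews about annually, or more often if it requires (7.4.2). The study may be suspended for unacceptable risk (13.1). This stands. A reader might infer that nothing in the plan could stop accrual in the Ruxience arm, and the documents do not support that. What is missing is a number.
- **The accrual sentence may already reach them.** In the 40 mcg/kg paragraph of section 10.2, the sentence on a third DLT does not itself restrict the count to ten, and section 3.1.3.1 defines dose level 2 by the moxetumomab dose alone. The setting (ten participants, rituximab, initial plan) favours the narrower reading, but it is an ambiguity. The more explicit wording, "at any time in the 10 participants, if a 3rd participant has a DLT, accrual will also end", belongs to the branch returning to 30 mcg/kg after DLTs at 40 mcg/kg. That branch was not used, so it should not be cited as settling the matter.
- **Ruxience safety data are analysed.** All participants are evaluable for toxicity (10.3.1), and section 10.4.4 covers DLTs and lesser toxicities. This also stands: the data will be seen. They simply do not feed the only pass/fail statement.
- **Ruxience is a biosimilar at a dose already tested.** Section 1.2.1 gives supporting comparisons, and section 10.4.3 expects no change. Yet 10.4.3 still compares the two groups on MRD-free CR before pooling them, and the primary endpoint has no corresponding step.

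**Conclusion.** The point holds for the primary conclusion. As written, the criterion in 10.4.2 cannot respond to 13 of the 26 participants, who are 13 of the 23 planned at 40 mcg/kg and everyone on Ruxience. It was effectively decided before that arm opened. This rests on the ten being those at 40 mcg/kg, and on there not being enough late DLTs to reach three among them. DLTs are evaluated throughout therapy (3.1.3.1), for up to 8 cycles plus 30 days after the last dose (3.1.2), so 0 of 9 was not final for anyone still on treatment.

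For accrual, the supportable statement is narrower: no numeric DLT limit clearly applies to participants 14-26.

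A reader might also infer that the plan treats a 45% DLT rate as unacceptable, and derive a pooled limit of 6 of 23 because its bound (41.3%) is the last one below 45.0%. The documents do not support this. The 45.0% is the confidence bound on 2/10, a result the plan accepts, and is nowhere called a threshold. Such a limit would also protect poorly. With none in the first ten it allows 6 of 13 on Ruxience, and at a true Ruxience rate of 45% it would be exceeded only 36% of the time (P(X ≥ 7) = 0.356 for n = 13).

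**What to change.** In section 10.4.2, base the primary safety conclusion on the DLT proportion with its exact one-sided 90% upper bound, reported (a) in all participants treated at 40 mcg/kg, planned 23, and (b) separately in the 13 on Ruxience. The method is the one already behind the 45.0% figure, and the data are already collected.

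Reconcile sections 3.1.3, 3.1.4, 10.2 and 10.4.2 so that they state whether and how the existing rule (no more than 2 of 10, with a third DLT ending accrual) applies to participants 14-26, including whether the count restarts or accumulates. Any threshold is for the sponsor to choose.

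The cost is about one paragraph, and a safety conclusion that could become less favourable. The documents do not show whether accrual is complete. If it is, the analysis change still applies, and the date it was made relative to the Ruxience data should be recorded.

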## 10.4.3 Analysis of the Secondary Endpoint(s)

- Response rates, MRD-free rates, and response durations will be reported descriptively, and the latter will be determined using Kaplan Meier Analyses.
- The MRD-free CR rates will be compared between evaluable participants on this trial and the 30 of 64 evaluable phase 1-3 participants who achieved MRD-free CR from moxetumomab pasudotox-tdfk using a Fisher's exact test, taking the interim results from this trial into consideration.
- The change from rituximab to Ruxience is not expected to result in a change to the CD20 Mab, and the comparison between participants 1-13 treated with moxetumomab pasudotox-tdfk rituximab and participants 14-26 treated with moxetumomab pasudotox-tdfk Ruxience will have limited power to detect a difference between rituximab and Ruxience in HCL. After enrollment of 26 participants, if the difference in MRD-free CR rate from moxetumomab pasudotox-tdfk rituximab vs moxetumomab pasudotox-tdfk Ruxience results is p>0.30 or higher, the results from the 2 groups will be considered close enough to be pooled and the full 26 participants could be compared against the 64 from the moxetumomab pasudotox-tdfk monotherapy studies.

Version Date: 04/16/2025

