#### • Administration:

- O Participants 1-13: Moxetumomab pasudotox-tdfk 30-40 mcg/kg intravenous (iv) over 30 min, rituximab 375 mg/m² iv, 50-400 mg/hr.
- o Participants 14-26: Moxetumomab pasudotox-tdfk 40 mcg/kg intravenous (iv) over 30 min, Ruxience 375 mg/m² iv, 50-400 mg/hr
- Rituximab or Ruxience day 1 (begin day -2 on cycle 1), Moxetumomab pasudotox-tdfk days 1, 3, and 5.
- Participants will receive up to 4 cycles past documentation of CR without MRD, maximum
   8.
- o To prevent renal toxicity and hypovolemia, participants will be encouraged to drink water gradually, approximately 1 cup/hour or 6L/day, not going >3 hours without drinking from days 1 to 8 and to keep a hydration diary to record daily fluid consumption.
- o To prevent rituximab/Ruxience toxicity, participants will receive prophylactic dexamethasone orally 0.5-2 hours before the 1st dose of rituximab/Ruxience, and before subsequent doses until rituximab/Ruxience infusion reactions are not seen. Participants will also receive diphenhydramine, famotidine and acetaminophen.
- O Dexamethasone 4 mg orally (maximum 2 doses/day) will be given as needed to treat nausea or fever associated with Moxetumomab pasudotox-tdfk, which might prevent adequate water intake

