# **Arm Assignment**

Participants in cohort 1 will be directly assigned to arm 1 or 2 in sequential fashion.

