# 10.4.5 Sub-Group Analyses

Not Applicable.

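### The rituximab-versus-Ruxience comparison has three 30 mcg/kg participants in one arm and none in the other, so a dose effect could mimic or mask a product difference; a 40 mcg/kg-only comparison should be added.

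*Combined protocol and SAP*

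**What the plan says.** Section 3.1.4 (Dose Expansion) records that the first 12 participants included "3 that received moxetumomab pasudotox-tdfk at 30 mcg/Kg and 9 at 40 mcg/Kg". It adds that "only 1 additional eligible participant treated with moxetumomab pasudotox-tdfk at 40 mcg/Kg could be enrolled, making a total of 13 eligible participants", so the rituximab arm ends as 3 at 30 mcg/kg and 10 at 40 mcg/kg. For the second arm, "an additional 13 eligible participants will be enrolled and treated with moxetumomab pasudotox-tdfk at 40 mcg/Kg in combination with Ruxience instead of rituximab"; the Précis agrees ("Participants 14-26: Moxetumomab pasudotox-tdfk 40 mcg/kg intravenous (iv) over 30 min, Ruxience 375 mg/m² iv"). Under Arm Assignment, participants are "directly assigned to arm 1 or 2 in sequential fashion", so nothing in the allocation balances dose.

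Section 10.4.3 takes "the comparison between participants 1-13 treated with moxetumomab pasudotox-tdfk rituximab and participants 14-26 treated with moxetumomab pasudotox-tdfk Ruxience" with no restriction, stratification or adjustment for dose. If the difference in MRD-free CR rate gives "p>0.30 or higher, the results from the 2 groups will be considered close enough to be pooled", all 26 may be set against the 64 monotherapy participants. The section concedes limited power for the arm comparison but does not mention the dose imbalance. Section 10.4.5 (Sub-Group Analyses) reads "Not Applicable", so no analysis by dose level is planned elsewhere.

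**The concern.** Three of 13 rituximab participants (23%) had a lower moxetumomab dose than every Ruxience participant. If the MRD-free CR rate depends on dose, the arms differ even when the two antibodies are identical. A lower rate at 30 mcg/kg pulls the rituximab arm down. If the antibodies are equal, this creates an apparent advantage for Ruxience. If Ruxience is really worse, it shrinks the visible gap and makes pooling of unlike groups more likely.

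The pooling decision matters because the plan's stated power belongs to the pooled 26. One arm of 13 tested alone against the 64 would have 49.4% power at 80% versus 47%.

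**Working it through.** **Inputs from the documents.** Arm 1 is 3 at 30 mcg/kg plus 10 at 40 mcg/kg, and arm 2 is 13 at 40 mcg/kg (section 3.1.4). The pooling threshold is p>0.30 (10.4.3). Section 10.2 gives 26 versus 64, 80% versus 47%, Fisher's exact test at one-sided 2.5%, power 79.8%, and an interim result of 7 MRD-free CRs among the first 9 evaluated.

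**Assumptions.** The pooling test is two-sided Fisher. The rate at 40 mcg/kg, p40, is 0.80, with 0.70 and 0.90 as a range. The rate at 30 mcg/kg, p30, runs from equal to p40 down to 0.30.

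**1. The plan's own figure.** Summing Bin(26, 0.80) × Bin(64, 0.47) over all outcomes with one-sided Fisher p ≤ 0.025 gives 79.81%. The stated 79.8% is reproduced.

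**2. Expected arm 1 rate with identical antibodies.** The rate is (3·p30 + 10·p40)/13. With p40 = 0.80:
- p30 = 0.60: (1.80 + 8)/13 = 75.4%, a spurious deficit of 4.6 points
- p30 = 0.47: (1.41 + 8)/13 = 72.4%, a deficit of 7.6 points
- p30 = 0.30: (0.90 + 8)/13 = 68.5%, a deficit of 11.5 points

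**3. Probability of refusing to pool, identical antibodies.** Arm 1 is Bin(3, p30) + Bin(10, p40) and arm 2 is Bin(13, p40). The sum runs over all outcomes with two-sided Fisher p ≤ 0.30. The last column uses Bin(10, p40) against Bin(13, p40).

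| p40 | p30 = p40 | p30 = 0.60 | p30 = 0.47 | p30 = 0.30 | 10 vs 13, all at 40 mcg/kg |
|---|---|---|---|---|---|
| 0.70 | 13.6% | 14.2% | 15.6% | 18.5% | 19.3% |
| 0.80 | 11.0% | 12.6% | 14.7% | 18.7% | 19.2% |
| 0.90 | 7.3% | 12.7% | 16.6% | 22.9% | 14.3% |

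**4. Masking.** Let Ruxience truly give 50% against 80% for rituximab at 40 mcg/kg. The 13-versus-13 check refuses pooling 57.8% of the time with no dose effect, 41.0% at p30 = 0.47 and 32.8% at p30 = 0.30. The 10-versus-13 comparison refuses 56.4% whatever p30 is.

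**5. One outcome that flips the decision.** Take 1/3 at 30 mcg/kg and 9/10 at 40 mcg/kg in arm 1, and 13/13 in arm 2.
- All participants, 10/13 versus 13/13: the chance that all three failures fall in arm 1 is C(13,3)/C(26,3) = 286/2600 = 0.11, doubled for two sides: p = 0.22. Do not pool.
- 40 mcg/kg only, 9/10 versus 13/13: there is one failure among 23, with probability 10/23 of falling in arm 1. The opposite table (13/23) is more probable and does not count, so p = 0.43. Pool.

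This fits the interim result: 1/3 plus 6/6 is 7/9, followed by 3 of the remaining 4 at 40 mcg/kg.

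**6. Historical comparison restricted to 40 mcg/kg.** The calculation in step 1 with 23 versus 64 gives 75.1% power.

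**The case against.** The strongest objection is to substituting a 10-versus-13 test for the planned pooling check. Such a test would pool 80.8% of the time under equal rates at 80%, against 89.0% now, and it refuses more often than the planned check at every p30 shown in the 0.80 row. Conditioning on the interim result points the same way. Suppose the three lower-dose participants are among the nine, and the remaining four rituximab participants and all Ruxience participants respond at 80%. The planned check then pools 94.7% of the time; the matched one pools 73.9%, 89.1% or 82.2% if 1, 2 or 3 of the three responded. This objection stands, so the planned check should stay.

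The interim result also limits how extreme the dose effect can be. The 30 mcg/kg participants were treated first and are very probably among the nine, although section 10.2 does not split them by dose. If they are, at most two of the three failed.

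A reader might infer that the 26-versus-64 comparison is invalid because three participants lie below the historical 40-50 mcg/kg range. The documents do not support that. Section 10.2 openly states the efficacy question for 30-40 mcg/kg, and if the lower dose is less active, including those three works against the combination.

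Finally, 10.4.3 uses the arm comparison mainly as a screen for pooling, expects no product difference and admits low power. That is fair, but the same comparison is the only one planned between the products, and the imbalance is not disclosed.

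**Conclusion.** The point holds as a low-cost improvement. Dose is partly confounded with antibody in 10.4.3 and can push the result in either direction. Under the assumptions of two-sided Fisher and 80% at 40 mcg/kg, false refusals to pool rise by about 2 to 8 points for 30 mcg/kg rates of 60% down to 30%. Masking is the larger effect: at 30 mcg/kg rates of 47% or 30%, the chance of refusing to pool a truly inferior product drops by about 17 or 25 points.

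A reader might go further and conclude that a dose effect exists, or that the pooling rule is likely to fail because of these three participants. Neither follows. No rate by dose is reported, the pooling test is unnamed, and the average shift in false refusals is modest. Matching on dose also does not isolate the antibody, because the arms were filled one after the other.

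**What to change.** Keep the planned 13-versus-13 pooling check and the 26-versus-64 comparison. Add to 10.4.3:

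- **(a)** The rituximab-versus-Ruxience comparison among participants treated at 40 mcg/kg only (10 versus 13), as a rate difference with an exact confidence interval, with the three 30 mcg/kg outcomes listed separately. Any statement about a difference between the products should rest on this analysis.
- **(b)** A sensitivity analysis of the 23 participants at 40 mcg/kg against the 64, reported beside the planned comparison, with its power of 75.1% at 80% versus 47%.

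The p>0.30 check should not be moved to 10 versus 13. The cost is a short addition to 10.4.3 and one extra table, all from data already collected. The matched estimates are less precise, the 23-participant analysis has 4.7 points less power (79.8% − 75.1%) if both doses work equally well, and confounding by calendar time is untouched. No change to dosing or enrolment is implied.

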• Sample size determination for amendment dated 9/21/2021: As of July 2021, a total of 12 participants were enrolled without DLT up to that point, making it likely that 3 participants will be enrolled with moxetumomab pasudotox-tdfk 30 mcg/kg and rituximab 375 mg/m², and 10 with moxetumomab pasudotox-tdfk 40 mcg/kg and rituximab 375 mg/m². Of the first 9 participants so far evaluated for response, 7 (78%) achieved CR, all MRD-free.

Given the encouraging safety and efficacy data from the phase 1 trial, it is desirable to increase the number of participants to gain more experience with moxetumomab pasudotox-tdfkand rituximab and be able to determine whether the efficacy of the combination at 30-40 mcg/kg of moxetumomab pasudotox-tdfk is better than our historical experience of 40-50 mcg/kg of moxetumomab pasudotox-tdfk alone tested for MRD at NIH. Historically, 30 of 64 evaluable phase 1-3 participants treated with moxetumomab pasudotox-tdfk alone achieved MRD-free CR assessed by bone marrow aspirate flow.

To enable additional participants to be enrolled affordably, starting with participant 14, participants will receive the biosimilar Ruxience instead of rituximab. Moxe-R thus represents the combination of moxetumomab pasudotox-tdfk with either rituximab or Ruxience.

If we are being conservative, the 7 of 9 participants who achieved MRD-free CR to date on Moxe-R would need to be considered an interim evaluation and its successful result would be the basis for deciding to add more participants. As such, it would be statistically appropriate to aim for a 0.025 one-sided test between 30/64 and the participants on the current trial. With a total of 26 evaluable participants on Moxe-R and 64 prior participants, a Fisher's exact test with a one sided 2.5% significance level will have 79.8% power to detect a difference between 80% MRD-free CR rate on the present trial and 47% from the 30/64 participants in the prior trials.

While a total of 26 evaluable participants will be enrolled, the accrual ceiling will be set at 30 to include screen failures and inevaluable participants.

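### The stated 79.8% power for 26 vs 64 takes no account of the p>0.30 pooling condition; with a two-sided Fisher gate, the chance of pooling and rejecting is about 71.5%

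*Combined protocol and SAP*

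**What the plan says.** Section 10.2 (amendment dated 9/21/2021) sizes the expansion on the MRD-free CR comparison. It sets 26 evaluable Moxe-R participants against the 64 treated earlier, and says that "a Fisher's exact test with a one sided 2.5% significance level will have 79.8% power". The target is a "difference between 80% MRD-free CR rate on the present trial and 47% from the 30/64 participants in the prior trials". The same section defines Moxe-R as moxetumomab with either antibody, so the figure is for all 26 together.

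Section 10.4.3 describes this comparison twice:

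- The second bullet compares the trial's evaluable participants with 30/64 by Fisher's exact test. It allows for the interim results but sets no pooling condition.
- The third bullet concerns participants 1-13 (rituximab) and 14-26 (Ruxience). It concedes that this comparison "will have limited power to detect a difference between rituximab and Ruxience in HCL". It then says that if the difference between the two groups' "results is p>0.30 or higher, the results from the 2 groups will be considered close enough to be pooled". Only under that condition does it add that "the full 26 participants could be compared against the 64 from the moxetumomab pasudotox-tdfk monotherapy studies".

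The third bullet does not name the test behind the p-value or say whether it is one- or two-sided. It does not say what is done when p is 0.30 or less.

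**The concern.** The 79.8% holds if all 26 are tested whatever the two groups look like. The third bullet adds a step that can stop the pooling, and Section 10.2 makes no allowance for it. The plan itself expects no change from switching product. If that is right, every gate failure is chance, and each one takes the trial off the comparison it was sized for.

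Detecting an improvement over 30/64 is one of the stated reasons for enlarging the trial, and 79.8% is the figure offered in support. With two descriptions of one comparison and no rule for the unpooled case, the analysis could end up being chosen after the data are seen.

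The gate is also a weak check of similarity. Thirteen per group is too few for a p-value above 0.30 to show that the groups are alike, as the plan's own remark on power implies.

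**Working it through.** **Inputs.** From Section 10.2: 26 vs 64, true rates 80% and 47%, one-sided Fisher's exact test at 0.025. From Section 10.4.3: groups of 13 and 13, pooling if p>0.30. The gate's test is an assumption. Two-sided Fisher is taken as the main case, because Fisher is the only test the plan names for comparing rates.

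**1. Reproduce the stated power.** Let T ~ Bin(26, 0.80) and C ~ Bin(64, 0.47). Sum P(T=t)·P(C=c) over all pairs with one-sided Fisher p ≤ 0.025. The result is 0.798, which is the plan's figure, obtained with no gate.

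**2. Chance that the gate passes when the arms are the same.** Let X and Y be independent Bin(13, 0.80). Sum P(X=x)·P(Y=y) over the 14 × 14 outcomes with gate p > 0.30.

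**3. Chance of pooling and rejecting.** Restrict the sum in step 1 to outcomes that pass the gate, with t = x + y.

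| Gate test | P(pool) | P(blocked by chance) | P(pool and reject) |
|---|---|---|---|
| None (Section 10.2) | 1 | 0 | 79.8% |
| Fisher two-sided, or continuity-corrected chi-square | 89.0% | 11.0% | 71.5% |
| Uncorrected chi-square, or one-sided Fisher | 66.7% | 33.3% | 52.5% |

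Under the Fisher gate the loss is 79.8 − 71.5 = 8.3 points. Among trials that do pool, power is 0.715/0.890 = 80.3%, so the whole loss comes from the trials that are not pooled.

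**4. Effect of a fallback.** Suppose an unpooled trial tests the rituximab 13 alone against the 64 at one-sided 0.025. Under the Fisher gate this adds about 5.5 points: 71.5 + 5.5 = 77.0%. A single arm is a weak substitute. Against exactly 30/64 it needs at least 11/13, and P(X ≥ 11 | 13, 0.80) = 0.502.

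**5. A strong result that the gate would block.** With 13/13 and 10/13, the two-sided Fisher gate gives p = 0.22, so the groups are not pooled. Yet 23/26 against 30/64 gives one-sided p = 0.0002.

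**6. The gate as a similarity check (two-sided Fisher).** Probability of pooling when the arms truly differ:

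- 80% vs 60%: 64%
- 90% vs 60%: 39%
- 80% vs 47% (one arm no better than monotherapy): 36%

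**7. Type I error.** With all true rates at 47%, P(pool and reject) is 1.3% under the Fisher gate and 1.1% under uncorrected chi-square, both below the nominal 2.5%.

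**The case against.** The strongest reply is that the third bullet says the 26 could be compared if p>0.30. It does not say that the comparison is dropped otherwise, and the second bullet commits to it without condition. This stands in part. A reader might infer that the efficacy question goes untested when the gate fails, but the documents do not say so. What they contain is two descriptions that do not agree and no rule for the unpooled case. The 71.5% therefore counts an unpooled trial as not reaching the planned test, and a stated fallback would recover some of the loss.

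A reader might also infer that power falls to 52.5%. That requires an uncorrected chi-square (or a one-sided Fisher) gate. Nothing in the plan points to either, and with 13 × 0.20 = 2.6 expected non-responders per group an uncorrected chi-square would be a poor choice.

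It is tempting to use the pooling of dissimilar arms as a reason to delete the gate. It is not one, because always pooling would pool a true 90% vs 60% split every time instead of 39% of the time. The case for an unconditional comparison is that it delivers the stated power and removes the ambiguity. Similarity is better shown by an interval.

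Finally, the plan openly discloses the limited power of the arm comparison, the trial's primary objective is safety, and the gate does not inflate type I error. All of this stands and limits the weight of the point.

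**Conclusion.** The point holds in a limited form. Section 10.2's 79.8% does not describe the procedure in the third bullet of Section 10.4.3. With both arms truly at 80%, monotherapy at 47% and a two-sided Fisher gate, the probability of pooling and rejecting is about 71.5%, or about 77% if unpooled trials fall back on the rituximab arm alone. The first figure assumes that an unpooled trial makes no further test. The documents neither state nor exclude this. Passing the gate is weak evidence that the two groups are alike.

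This should be fixed, but it does not threaten the trial. It concerns a secondary, historically controlled comparison and leaves the DLT-based primary endpoint untouched.

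**What to change.** In Section 10.4.3, remove the p>0.30 condition and make all evaluable participants (planned 26) vs 64 the prespecified comparison in every case. The second and third bullets then agree and 79.8% stands. Report each arm's MRD-free CR rate, and the rituximab-minus-Ruxience difference with an exact 95% CI, descriptively. This costs about two sentences and no participants or procedures. The downside is that the pooled test is reported even when the arms look different; the interval will show that.

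If the gate is kept, name its test (two-sided Fisher), prespecify the analysis when p is 0.30 or less, and restate the power in Section 10.2. The figure would be about 71.5% for pooling and rejecting, or the value recomputed with the chosen fallback (about 77% for the rituximab arm alone).
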